3. Abstract: With modern therapies, people living with HIV (PLWH) show a life expectancy approaching that of the general population. However, PLWH are affected by non-HIV-related comorbidities, including myocardial infarction and cancer, which typically occur earlier than in otherwise healthy individuals. These comorbidities appear to be strongly related to chronic inflammation and pain, conditions that often characterize PLWH. Phyto-cannabinoids such as cannabidiol (CBD), available on-line and in many grocery stores in the US, are known to have anti-inflammatory and analgesic properties. The intra-cellular mechanisms and pathways that cannabinoids use to alter inflammation and pain, however, are yet to be fully understood. Our objective will be to conduct a highly innovative pilot clinical study that investigates the therapeutic effects of a CBD-rich oil administration under the tongue on mechanisms and processes that underlie chronic inflammation and pain associated with PLWH. Our preliminary results show (a) different sub-types of pro-inflammatory monocytes emerging from single-cell RNA sequencing (scRNAseg) data in an inflammation model, and (b) an enrichment in MAPK-signaling pathways in microarray transcriptional profiling from PLWH using cannabis. More specifically, to investigate the presence of pro-inflammatory cell populations, we utilized the data from our previous work, a mouse model based on trauma [0], and considered monocytes both at baseline (uninjured, day 0) and inflammation peak (burn/tenotomy, day 3). We found the emergence of a specific pro-inflammatory monocyte population (Figure 1). The trauma model generates a post-wound inflammatory peak at day 3. Monocytes were identified by unsupervised clustering and marker analysis, validated by automated labelling of state-of-the-art algorithm SingleR10. We found six monocyte clusters (labeled 0 to 5, Figure 1, B and C). For each cell, we calculated an inflammatory score based on the fraction of the counts per cell (over its total counts) associated with the Gene Ontology term "regulation of inflammatory response" (GO:0050727), including 556 mouse genes. Different clusters (Figure 1, A) have a different inflammatory profile, with 0 and 4 showing a low inflammatory profile; clusters 1, 2, and 3 a high inflammatory profile; and cluster 5 very high inflammatory profile, mostly composed by monocytes on day 3. We compared high and very high inflammatory transcriptome profiles versus low

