The main objective of this project will be to identify inflammatory reduction biomarkers linked to MAPK-dependent alterations after CBD administration, as well as other systemic effects on cell signaling pathways. Investigating the role of cell-specific biomarkers describing the molecular response to CBD-administration may open avenues for additional therapeutic strategies that can help reduce the burden of chronic musculoskeletal pain and other pain-related symptoms and comorbidities in people living with HIV (PLWH). The team proposes to study the effects of CBD on inflammation and chronic pain in PLWH by enrolling five persons with HIV who will provide blood samples before and after taking CBD for two months. In the process, the goal will be to establish the molecular role(s) of different immune cells using single cell RNA-sequencing. Preliminary data from this study are expected to pave the way for further investigations in larger clinical cohorts. The primary aim of this project will be to identify key inflammatory reduction biomarkers linked to MAPK-dependent alterations after CBD administration. Secondary outcomes include pain relief and reductions in pain-related symptoms. We will use a prospective pilot study design where patients will self-administer the investigational product (CBD-extract) for 60-days (2 months).

Specific Aim #1 – Determine the effects of CBD on chronic on quality of life in PLWH. We will compareQuality of Life (QoL) measures between treatment conditions, including pain and pain-related symptoms, if present.

Specific Aim #2 – Determine key biobehavioral mechanisms contributing to antiinflammatory and analgesic effects of CBD administration in PLWH. We hypothesize that change in molecular (alterations in cell signaling and reduction in inflammatory cytokines), psychological (reduction in pain-related fear and pain catastrophizing), and pain sensitivity regulation measures will be associated with pain relief, inflammation reduction, and reservoir shrinkage. We will quantify the shift in anti-inflammatory macrophage/monocyte population caused by CDB administration by examining gene expression at the single-cell level from the PBMC samples. This will allow us to accurately pinpoint gene under- or over-expression patterns at the RNA level (biomarkers), that are both induced by CBD administration in PLWH, and specific to different cells (e.g., monocytes, T cells, B cells, or other immune cells).

6. Research Plan

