CBD biomarker extraction. We will contrast clusters of the same cell type at baseline (no CBD) and their counterparts after CBD administration. The difference in gene expression, measured in fold change, p-value, and ratio of cell fraction expressing the marker gene, will determine the phenotypic effect of CBD. For each cell type, we expect to extract one or more sets of CBD-specific candidate biomarkers that together will determine a phenotypic CBD per cluster (cell type) signature.

Investigational Product & Dosing Schedule. [name] (Co-I) will oversee CBD dosage and administration.We will source the investigational product from the same batch of our hemp-extract CBD product that is being used in the original protocol under IND 147985, 'Efficacy of a controlled short-term trial of Cannabidiol (CBD) ingestion on reducing symptomatic response and facilitating recovery after induced muscle injury' (Source: SunFlora, Inc, [name])''. SunFlora is a third-party tested hemp-derived product manufacturing company. SunFlora is dedicated to producing high quality hemp-derived products formulated to be safely used by the public and are manufactured in accordance with the Food and Drug Administration (FDA) Current Good Manufacturing Practices (cGMP) for Dietary Supplements, 21 CFR Part 111. Their hemp derived products are assessed multiple times at production process control points throughout the manufacturing process. Dietary ingredients used in the manufacturing process are accompanied by certificates of analyses (CoAs) confirming their identity and specifications. All finished products are tested to ensure they meet specifications prior to being released for distribution. The label and all labeling satisfy FDA requirements found under 21 CFR 101.

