Primary Outcomes: This study takes a single-cell perspective, i.e., we will collect a large number of cells from a small number of patients, and we will measure RNA expression per single cell (not per patient). Note that from the single cell point of view, the number of patients (5-7) is sufficient to derive statistically viable results, as we will collect 5,000 cells from each patient at each time point (total 75,000-105,000 cells). Each cell will be sequence individually to read the RNA expression from a panel of approximately 20,000 genes. Cells will be pooled from all patients, and clustered via unsupervised algorithms into clusters of different cell types (e.g. T cells, B cells, monocytes). Our primary outcomes will be the extraction of gene expression patterns (RNA) from specific immune cell types found in PBMC (e.g., B cells, T cells, monocytes). We will regress these gene markers against the variation in baseline inflammation (C-reactive protein, erythrocyte sedimentation rate, and procalcitonin). After CBD administration to obtain CBD-related biomarkers for inflammation reduction. The difference in gene expression will be measured in fold change, p-value, and ratio of cell fraction expressing the marker gene. These biomarker gene will be unique for each cell type. We expect to extract specific biomarkers for each cell type and understand how CBD alters gene expressions of different immune cells in a different way-overall, we expect the genes of the MAPK signaling pathway (MAPK families play an important role in complex cellular programs like proliferation, differentiation, development, transformation, and apoptosis) to be strongly altered.

Secondary Outcomes. Self-report pain ratings will be used to determine peak pain intensity and pain persistence. The brief pain inventory (BPI) will be used to self-report pain perception. The inventory consists of rating pain on a visual analog scale (VAS). A 10cm line is drawn with 0 (no pain) on the left pole and 10 (worst pain imaginable) on the right pole. The inventory asks participants to rate their level of pain by placing a slash on the line that best represents their current level of pain as well as pain at its worst, best and average over the past 24 hours. The highest worst pain intensity reported during the intervention will be recorded as the peak pain intensity.

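### The CBD contrast does not fix the cluster level and has no before/after comparison of monocyte shares, so Aim 2's population shift could be missed or confused with altered expression

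*Combined protocol and SAP*

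**What the plan says.** In section 6, Primary Outcomes describes how clusters are formed: "Cells will be pooled from all patients, and clustered via unsupervised algorithms". The pooled set includes cells from baseline and from both post-CBD visits.

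CBD biomarker extraction then defines the comparison: "We will contrast clusters of the same cell type at baseline (no CBD) and their counterparts after CBD administration". The difference in expression, "measured in fold change, p-value, and ratio of cell fraction expressing the marker gene, will determine the phenotypic effect of CBD". Primary Outcomes repeats these three measures. Neither section mentions the share of cells in each cluster.

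Specific Aim #2 (section 5) sets a target that concerns shares: "We will quantify the shift in anti-inflammatory macrophage/monocyte population". It says this will be done through single-cell gene expression and names no estimator.

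On cluster level the text points two ways. CBD biomarker extraction equates cluster with cell type, in results "that together will determine a phenotypic CBD per cluster (cell type) signature", and Primary Outcomes has cells "clustered via unsupervised algorithms into clusters of different cell types (e.g. T cells, B cells, monocytes". The preliminary mouse data in the Abstract (section 3) instead divide one cell type: "We found six monocyte clusters (labeled 0 to 5, Figure 1, B and C". Those clusters differ in inflammatory profile, with "cluster 5 very high inflammatory profile, mostly composed by monocytes on day 3".

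Data analysis (section 6) says clusters will be annotated so that the cell composition of each sample can be described. It gives no comparison of composition over time.

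**The concern.** Clusters are formed from expression in a pool that includes treated cells, so a cell that changes state can change cluster. Cluster membership is then a post-treatment variable, and comparing like cluster with like cluster conditions on it. If CBD moves monocytes from inflammatory to non-inflammatory states, the cells left in each state may look the same before and after. The effect then lies in the shares, which the plan does not compare.

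At stake is one of the effects the trial is meant to detect. The central hypothesis in Background (section 4) is that CBD hinders pro-inflammatory monocytes, and Aim 2 promises to quantify a population shift. As specified, the analysis could return a null result when such a shift has occurred, or report it as altered gene expression when expression within each state has not changed.

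**Working it through.** **The plan's own figure.** Patients × time points × cells per sample: 5 × 3 × 5,000 = 75,000 and 7 × 3 × 5,000 = 105,000. This agrees with the stated total. The plan gives no monocyte share, expression difference or expected shift, so the values below are assumptions chosen to show the mechanism.

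**Pure shift between states.** Let a fraction p of monocytes be inflammatory at baseline, with mean expression k of a gene; the others have mean 1. Half of the inflammatory cells take on the non-inflammatory state, and expression within each state does not change.

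- Within each state: fold change = k/k = 1/1 = 1.00.
- Over all monocytes: fold change = [1 + (p/2)(k − 1)] / [1 + p(k − 1)].
- With p = 0.40, k = 4: before, 0.6 × 1 + 0.4 × 4 = 2.2; after, 0.8 × 1 + 0.2 × 4 = 1.6; ratio 1.6/2.2 = 0.73 (log2 −0.46).
- Largest change in the range, p = 0.50, k = 4: 1.75/2.50 = 0.70.
- Smallest change in the range, p = 0.30, k = 2: 1.15/1.30 = 0.88.

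**Why the lineage-level figure is ambiguous.** Keep the shares at 60% and 40%, and let expression in inflammatory cells fall from 4 to 2.5. The mean after treatment is 0.6 × 1 + 0.4 × 2.5 = 1.6, and the ratio is again 0.73. A change of shares and a change of expression within cells give the same all-monocyte fold change. The ratio of inflammatory to non-inflammatory cells separates them: in the first case it goes from 0.4/0.6 = 0.667 to 0.2/0.8 = 0.25, a factor of 0.375; in the second it stays at 0.667.

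**Simulation with other assumed values.** Means were 4 and 1 (Poisson), monocytes made up 10% or 20% of 5,000 cells per sample, there were 7 patients and 300 runs, and a two-sample t-test on cells was used at 0.05. The inflammatory share fell from 60% to the value shown.

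| Share after CBD | Fold change within state | Fold change, all monocytes | Expressing-fraction ratio, all monocytes |
|---|---|---|---|
| 50% | 1.00 | 0.89 | 0.96 |
| 40% | 1.00 | 0.79 | 0.92 |
| 30% | 1.00 | 0.68 | 0.88 |

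Within states, the test rejected in 3-7% of runs, which is about the null rate. Over all monocytes it rejected in 100%. These rates treat cells as independent; they show the mechanism only and are not valid error rates for 5-7 patients.

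**What a patient-level share comparison can deliver.** The smallest two-sided exact signed-rank p is 2/2^n: 0.0625 for n = 5, 0.031 for n = 6 and 0.016 for n = 7. Paired-t power at an assumed alpha of 0.05, for assumed shifts of 1.0, 1.5 and 2.0 within-patient SDs, is 0.40, 0.71 and 0.91 with 5 patients, and 0.60, 0.91 and 0.99 with 7.

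**The case against.** A reader might infer that the planned contrast is bound to show no change under the effect the trial was designed to find. The documents do not support that, for four reasons.

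- CBD biomarker extraction and Primary Outcomes both gloss cluster as cell type. If all monocytes form one cluster, the shift does appear, at 0.73 in the example.
- The six state clusters come from a mouse wound model. They show what this kind of workflow can produce, but no section says that the same resolution will be used for human PBMC.
- The shift is one hypothesised effect among several. Background and Motivation to study single cells also expect MAPK-dependent changes in monocyte phenotype and migratory capacity. Within-cell changes of that kind would be seen at either level.
- Each sample's composition will be characterised, so per-patient shares at each visit could be derived, and a cluster that empties after CBD would be noticed.

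All four stand as limits on the point. They do not remove it. The level is still not fixed, and describing composition is not a paired comparison over time. The cell-type reading replaces a missed effect with an ambiguous one.

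It is also fair to say that the 1.00 within each state follows by construction, because the example assumes no change within cells. In a pilot of 5-7 patients seeking candidate biomarkers, a share measure will be imprecise. That is a reason to report an interval rather than to omit the measure.

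**Conclusion.** The point holds in a limited form. The plan fixes neither the cluster level of the CBD contrast nor any before/after comparison of monocyte sub-population shares, so Aim 2's shift has no specified estimator. At sub-cluster level a pure shift gives a fold change of 1.00. At lineage level it gives 0.73 in the example (0.70 to 0.88 over the range considered), and the same figure can arise from altered expression with unchanged shares.

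These sizes rest on assumed shares of 30-50%, 2- to 4-fold expression differences, half of the inflammatory cells moving, and no change within states. The direction of the argument does not depend on the exact values. The plan should be changed, because a better analysis is available on data it already collects.

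**What to change.** In CBD biomarker extraction and Primary Outcomes, state that the main contrast is at lineage level (all monocytes, T cells, B cells). Assign lineages by fixed marker or reference labelling, and use counts aggregated per patient and visit, paired by patient. Keep within-cluster contrasts as secondary.

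For Aim 2, add one pre-specified measure: each patient's change, from baseline to a named post-CBD visit, in the log-ratio of inflammatory to non-inflammatory monocytes. Fix the rule for calling a monocyte inflammatory beforehand. Compute the ratio within monocytes, so that it does not depend on what share of the 5,000 cells they make up. Add a small count offset so that it is defined if a sub-cluster empties. Report an estimate with an interval rather than relying on a test, since with 5 patients a two-sided signed-rank test cannot reach 0.05.

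The cost is revised analysis wording and a little more analysis; no further samples, visits or sequencing are needed. The downside is that lineage-level contrasts mix state and composition, so they must be read together with the share measure.

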Overview and Rationale for Study. Inflammation is a primary HIV-related complication. HIV patients experience non-AIDS-related complications that are typical of older patients, such as presence of neurocognitive disorders, metabolic syndrome, bone abnormality, non-HIV-associated cancers, and neurocognitive disorders [1]. Chronic inflammation in PLWH is a significant problem that impacts the quality of life in PLWH. The effects of cannabinoids in reducing inflammation are renowned; however, the intra-cellular mechanisms and pathways that cannabinoids use to alter inflammation are yet to be discovered. Our central hypothesis is that CBD is an extremely beneficial therapeutic drug for PLWH, because it reduces inflammation by hindering pro-inflammatory monocytes via MAPK-dependent pathways. This hypothesis targets two fundamental unanswered problems in the field of HIV/AIDS, that are high HIV/AIDS NIH priorities: (i) identifying the mechanism regulating PLWH persistent inflammation, which in turn plays a pivotal role in all the main causes of death in PLWH; and (ii) investigating the role of cell-specific candidate biomarkers describing the molecular response to CBD, which may open for new cure strategies.

By mapping the effects of a controlled trial of CBD-administration at the single-cell level, we will pave the way for new candidate therapies, from CBD- and other cannabis-based therapies to the identification of novel protein targets for drug repurposing or discovery. Understanding how CBD reverses inflammation (potentially at the systemic level), will help overcome a significant challenge for HIV care and treatment, particularly for infected young adults who have a lifetime in combined antiretroviral therapy (cART). Filling this gap is particularly relevant because our findings will provide a framework for the evolving policies for clinical use of FDA-approved drugs for HIV cure strategies. As such, it has an enormous repercussion as THC is not legalized for its psychoactive properties, while CDB can be found in any grocery store in the US. Therefore, understanding CBD influence on HIV-induced inflammation is also extremely important to inform the medical community and the public answering which compound has a therapeutic validity. Our findings will potentially open a new therapeutic window for personalized and precision medicine.

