Motivation to study single cells. The molecular and cellular changes underlying the inflammation mitigation caused by CBD-administration are largely unknown, and stand as a major challenge both for understanding its basic biology (e.g., pathways involved, molecular mechanisms) and for the urgent unmet need of reducing the long-term harm chronic inflammation causes in PLWH. Our hypothesis is that CBD alters monocyte migration capacity with MAPK-dependent alterations. We expect this alteration to have

chain-effects based on cellular cross-talk, i.e., that different PBMC cell types (such as Tcells and B-cells) might express specific CBD-induced phenotypes. We hypothesize CBD-alterations to reverberate along the whole immune-modulation system through cellular cross-talk. Given the complexity of the immune response, we deem traditional (bulk) RNA sequencing as insufficient for the task. Population-averaged genomic profiling cannot adequately unravel the inter-cellular regulation in situ. This study will leverage the efficiency of newly available single-cell technologies to create a powerful dataset unveiling the functional properties of thousands of individual cells.

Sample collection and processing. We plan to collect samples from five to seven patients over three time points: baseline (no CBD), and after one and two months of CBD-administration with 5,000 cells sequenced per sample. Five to seven patients (15 to 21 samples) will provide the transcriptomes of 75,000-105,000 single cells, a large dataset for scRNAseq. Immediately after collection, samples will be collected by TBD Lab technician to be processed for scRNAseq at UF ICBR (PBMC scRNAseq experiments are routinely run at ICBR).

Data analysis. During the post-processing period, single-cell reads (count matrices) will be filtered for quality control. Unsupervised clustering will isolate statistically robust populations of similar cells. Clusters will be visualized using Principal Component Analysis (PCA), t-Distributed Stochastic Neighbor Embedding (tSNE), and Uniform Manifold Approximation and Projection (UMAP). The most informative gene expression markers will be identified by a host of non-parametric tests (e.g., the Kolmogorov–Smirnov test), comparing a given cluster against either a nearby cluster or all other clusters. Clusters of cells will be annotated by using their marker genes/pathways⁻ and prior biological knowledge to characterize each sample's cell composition.

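### A single-arm before-after pilot cannot separate CBD from time, yet the plan reads its before-after differences as the effect of CBD and calls the study controlled

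*Combined protocol and SAP*

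**What the plan says.** **Design.** Section 5 describes the study in these words: "We will use a prospective pilot study design where patients will self-administer the investigational product". It speaks of "enrolling five persons with HIV who will provide blood samples before and after taking CBD for two months". Sample collection and processing (Section 6) sets the time points at "baseline (no CBD), and after one and two months of CBD-administration with 5,000 cells sequenced per sample". Visits 1 to 3 under Experimental Procedures give every participant the same product on one daily regimen. No placebo, untreated group, randomisation, blinding, repeat baseline or off-drug sample is described. The only contact after visit 3 is a safety phone call one week later.

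**Claims.**
- CBD biomarker extraction (Section 6): the baseline versus on-CBD difference, including the ratio of cells expressing the "marker gene, will determine the phenotypic effect of CBD".
- Specific Aim 2 (Section 5): expression patterns are "induced by CBD administration", and the macrophage/monocyte shift is likewise described as caused by CBD.
- Primary Outcomes (Section 6): the same expression differences are expected to show how CBD alters gene expression in each cell type.
- Background (Section 4): "By mapping the effects of a controlled trial of CBD-administration at the single-cell level".
- Specific Aim 1 (Section 5): quality-of-life "measures between treatment conditions, including pain and pain-related symptoms, if present". The conditions are not defined.

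**The concern.** The contrast in the plan is after minus before, in patients who all know they are taking CBD. Anything else that changes between visits falls into the same difference. The documents themselves point to several candidates:

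- **Expectation.** Pain, pain anxiety, sleep and SF-12 are self-reported and no blinding is described.
- **Intercurrent illness.** C-reactive protein, erythrocyte sedimentation rate and procalcitonin are the inflammation measures. The plan does not say how a new infection between visits would be handled.
- **Cannabis use during follow-up.** The Background reports MAPK-pathway alterations in recreational users, which is the signal expected from CBD. The urine drug test is listed at visit 1 only.
- **Processing batch.** Samples go for processing straight after collection and no balancing across runs is described. That run follows visit is an inference, since the documents do not say how runs are composed.

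What is at stake is the conclusion. Followed as written, the plan attributes these changes to CBD by rule. The Background expects the findings to inform clinical-use policy and the question of which compound has therapeutic validity.

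**Working it through.** **1. The plan's own figure.** Inputs, from Sample collection and processing: 5 to 7 patients, 3 time points, 5,000 cells per sample.
- 5 × 3 = 15 samples; 15 × 5,000 = 75,000 cells.
- 7 × 3 = 21 samples; 21 × 5,000 = 105,000 cells.

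This reproduces the plan's statement: "Five to seven patients (15 to 21 samples) will provide the transcriptomes of 75,000-105,000 single cells".

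**2. Samples by time and treatment.**

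| | No CBD | On CBD |
|---|---|---|
| Visit 1 | 5 to 7 | 0 |
| Visits 2 and 3 | 0 | 5 × 2 = 10 to 7 × 2 = 14 |

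The untreated follow-up cell is empty.

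**3. What can be estimated.** Write the mean response at visit j as a + τ_j + β·X_j, where X = 0, 1, 1 at visits 1, 2, 3 and τ_1 = 0. Here β is the CBD effect, and τ_2 and τ_3 are changes that would have occurred anyway.
- Visit 2 − visit 1 = τ_2 + β
- Visit 3 − visit 1 = τ_3 + β
- Visit 3 − visit 2 = τ_3 − τ_2, which does not contain β

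Only two of these contrasts are independent, and there are three unknowns. β appears only as a sum with τ. If the true CBD effect is β and the other change is d, the plan reports β + d as the effect of CBD. One could force a solution by assuming a linear time trend and a constant CBD effect from month 1. The plan makes no such assumption, and three visits leave nothing with which to check it.

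**4. Does sample size help?** The documents give no alpha, SD or effect size, so this step is an illustration on assumed inputs: β = 0, a paired two-sided test at 0.05, and a common non-drug shift d in units of the SD of within-patient change. The test statistic is noncentral t with n − 1 degrees of freedom and noncentrality d√n. The probability of declaring a difference is:

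| d (assumed) | n = 5 | n = 7 |
|---|---|---|
| 0 | 0.05 | 0.05 |
| 0.5 | 0.14 | 0.20 |
| 1.0 | 0.40 | 0.60 |
| 2.0 | 0.91 | 0.99 |

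For any non-zero d the probability rises with n. Larger numbers make a wrong attribution more likely.

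**The case against.** **The design is disclosed.** The plan says pilot, preliminary data, before and after, and candidate biomarkers. *Controlled trial* is applied to this study once, in background prose, and may mean supervised dosing as opposed to recreational use. The other *controlled* trial, named under Investigational Product, is the title of a different protocol. All of this is fair and softens the tone. It does not alter the rule in CBD biomarker extraction or the causal wording of Aim 2, and no passage states that dosing is the sense intended.

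**Some sources of drift are limited.** Entry requires at least five years of antiretroviral therapy and suppressed virus. Chronic infections, medicines affecting inflammation, and current marijuana or CBD use are excluded. These criteria reduce d by an unknown amount and do not replace a control.

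**The size is not established.** It is true of every uncontrolled study that d enters one for one, and the documents give no value for d. This stands: the table shows direction, not an estimate for this trial. The expectation argument also concerns the questionnaires, not the gene expression contrast.

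**Stronger readings that the documents do not support.**
- A reader might infer that Aim 1's comparison cannot be run. Sample collection and processing labels baseline as no CBD, and the visit schedule has questionnaires before CBD and again at visits 2 and 3. Read as no CBD versus CBD within patient, the comparison can be run. The fault is that the term is undefined.
- A reader might infer from the mention of low-dose or high-dose extract under Possible Benefits that dose groups exist. The procedures describe a single regimen, so those passages need reconciling but do not supply a comparator.
- A reader might infer that a larger controlled study is already planned. The documents say only that further work in larger cohorts may follow and that the data may be used to plan a larger trial.

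**Conclusion.** The concern holds for the claims made from the design. Time and CBD are fully confounded: 10 to 14 follow-up samples on CBD, none untreated, and one pre-CBD sample per patient. The plan's rule that the before-after difference is the effect of CBD, Aim 2's causal wording and the controlled-trial label each claim a property that this design does not have, and no limitation is stated. This rests only on the visit schedule and on the absence of any described comparator. Calling the study open-label is an inference from the absence of any described blinding. The amount of bias is unknown, and the probabilities shown depend on assumed shifts.

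It does not follow that CBD has no effect, that the pilot is without value, or that a control arm must be added. A single-arm pilot can properly report change during use. It cannot assign that change to the product.

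**What to change.** - **Section 6, CBD biomarker extraction, and Primary Outcomes where gene changes are attributed to CBD:** report change from baseline during CBD use instead of the effect of CBD.
- **Section 5, Specific Aim 2:** replace *induced by* and *caused by* with *observed during*.
- **Section 4, Background:** replace *controlled trial* with *single-arm before-after pilot*.
- **Section 5, Specific Aim 1:** replace the comparison between treatment conditions with within-patient change from visit 1 to visit 2 and from visit 1 to visit 3, each with a 95% CI.
- **Add a limitation:** attributing the changes to CBD would need a future study with a concurrent control.

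Cost: no new arm, visit, sample or patient. The stated claim becomes less favourable, and the confidence intervals for Aim 1 are a small added analysis.
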